5.2.1.5 Costs associated with HAE attacks

Costs will be estimated for HAE attack episodes, by severity and by treatment location (ED only vs inpatient for severe attacks and home versus office for non-sever attacks). Attack costs will be estimated by summing costs across the medical services utilized during an attack, excluding the costs of on-demand therapies, which are included in the cost-effectiveness model separately. Specific outputs will include:

- Outpatient care
 - Cost per attack treated with a home visit for on-demand treatment administration
 - Cost per attack treated with an office visit for on-demand treatment administration
- Cost per attack treated as ED visit
- Cost per attack treated as inpatient hospitalization

If sample size allows, cost analysis will be restricted to most recent years (2017 – 2020) in order to estimate the most timely and relevant costs. This will be a subgroup analysis of the prophylaxis initiation cohort.

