5.2.1.4 HAE attack rates

Observational studies that evaluate attack rates in claims or EHR data sets are limited. There is currently no validated method to evaluate HAE attacks in claims data.

In creating our definitions of severe and non-severe attacks, we took guidance from clinical experts, treatment guidelines, and published literature that identified symptoms ([Longhurst & Bork 2019](#))⁵ or used diagnoses codes indicative of an attack (Tachdjian 2020).¹ Symptoms and diagnoses codes were cross referenced in a de novo code search to capture both ICD-9 and ICD-10 codes.

Attacks are defined by severity:

- **Severe attack:** Treatment guidelines and empirical data suggest that severe attacks are typically treated in the ED.⁶ For this analysis, severe attack will be defined in two ways: broadly as all-cause ED visits with or without hospitalization and more specifically as HAE ED visits with or without hospitalization. HAE specific severe attacks will be defined by a claim for an ED visit with or without hospitalization that includes diagnoses and drugs indicative of an attack (see Annex 2).
- **Non-severe attack-** Non-severe attacks are treated with on-demand therapy either by self-administration or administration by a healthcare professional. An attack treated by a healthcare professional will be defined as a medical service claim for an on-demand therapy occurring outside an inpatient or ED setting (e.g., physician office). For self-administration, we will estimate the number of attacks treated by calculating the number of doses dispensed based on dispensed quantity and approved dosages. Based on [treatment guidelines](#),⁶ patients should readily have on-demand therapy to treat two attacks, thus we will consider any doses dispensed over the two on-hand dosages of on-demand therapy as evidence of an attack.

Data on the duration of attacks by severity is limited, however attacks generally last between two and five days.⁷ Thus, on-demand therapy administrations by a healthcare professional, ED visits, and inpatient hospitalizations occurring within five days of each other will be considered part of a single attack. In cases where an on-demand therapy administration occurs within five days of an ED visit or hospitalization, the attack will be counted as a severe attack.

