5.4 Statistical analysis

5.4.1.1 Baseline attack rates (primary objective)

Attack rates will be calculated as the total number of attacks in the cohort divided by the number of person-months during baseline (six months prior to initiation of prophylaxis treatment). The rates

and percentages of attacks by severity (severe all-cause, severe-HAE specific, non-severe) will also be calculated for the baseline cohort.

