5.4.1.3 Exploratory Follow-up descriptive analyses

Due to the small sample size, there is a lack of power to complete a formal pre/post analysis to detect a meaningful difference in attack rates. Thus, our follow-up analysis will be descriptive.

In the follow up period, we are interested in exploring the frequency of attacks after initiation of prophylaxis therapy, understanding utilization, and determining how many months patients were attack free after initiation. Follow up attack rates will be stratified by drug (Takhzyro, Haegarda, and Cinryze) and we will focus on severe attacks only. We will explore the following:

- Adherence to prophylaxis therapy
- Switching behavior between the three prophylaxis drugs
- Attack rates, including attack-free months

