Android Methitest Testred Virilon (Methyltestosterone)	NDCs: 00187-0902-01 00115-1408-01 00187-0901-01 00115-7037-01	Clinical Pharmacology Database²⁰
Winstrol (Stanozolol)	NDCs: 0024-2253-04??	Clinical Pharmacology Database²⁰
Prophylactic use of Cinryze and Ruconest	Algorithm and code lists	Source
Cinryze prophylactic use	Cinryze is indicated for prophylaxis, but is used off-label for acute attacks. Prophylactic use will be defined as continuous refills of Cinryze averaging ≥ 1500 IU/week for ≥ 90 days.	Riedl 2018²²
Ruconest prophylactic use	Ruconest is indicated for on-demand use, but is used off-label for prophylaxis. Patients with Ruconest prophylactic use will be excluded from the cohort. Prophylaxis use will be defined as continuous refills of Ruconest averaging 50 IU/kg once weekly for 90 days.	Riedl 2018²²
every four-week	Used to determine if a dose reduction occurred.	

administration of Takhzyro	This will be measured over a 90-day follow-up period based on total dose <= 1200 mg over that period. The 1200 mg is based on three 300 mg injections plus one additional injection to account for potential variation in exact timing.	
Attack severity	Algorithm and code lists	Source
Severe	
ED visit with/without hospitalization, identified based on “Type of service” coded as inpatient or emergency room. Events identified as HAE-specific include at least one of the following diagnose (as a primary diagnosis for hospitalizations /or treatments indicative of an attack:
 
 € Codes often associated with HAE: ICD-9-CM 277.6 or ICD-10-CM D84.1 € Angioedema diagnosis: ICD-9-CM 995.1 or ICD-10-CM T78.3* € Administration of on-demand HAE treatment € Diagnosis of swelling, abdominal pain, or asphyxiation: 
 o ICD-9-CM 518.81, 518.84, 787.0*, 782.2, 789.0*, 786.02, 786.05, 786.1 o ICD-10-CM J96.0*, J96.2*, J96.9*, R06.0*, R06.1, R10.*, R11.*, R22.0*, R22.1, R19.0 	
UpToDate states severe attacks are treated in ED.²³
 
Tachdjian 2020¹
 
Zilberberg 2010²⁴
 
Longhurst & Bork, 2019

Non- severe attack	
Each dose of an on-demand therapy over two acute attack doses is considered an attack. The number of doses dispensed will be calculated from the quantity dispensed and recommended dose and
 
Any on-demand therapy administered outside an inpatient or emergency room setting will be considered a non-severe attack.
	
Utilization	Algorithm and code lists	Source

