Annex 3: Results Table Shells

Table 1: Baseline characteristics of patients with HAE

Characteristic	RWE results	Notes	Prior ICER review base case	Prior ICER review source
Mean age			39.63	Banerji et al. 2017, ³⁰ Longhurst et al. 2017, ³¹ Zuraw et al. 2010 ³²
Female, %			68.4%	Banerji et al. 2017, ³⁰ Longhurst et al. 2017, ³¹ Zuraw et al. 2010 ³²
Mean weight, females			76.4	Fryar et al. 2016 ³³
Mean weight, males			88.8	Fryar et al. 2016 ³³
List of top 10 non-HAE therapies (therapeutic class)				

Table 2: Attack rates, utilization, and costs in the six-month baseline period before initiation of prophylaxis treatment

Characteristic	RWE results	Notes	Prior ICER review base case	Prior ICER review source
ATTACK RATES AND TREATMENTS ADMINISTERED				
Mean attack rate per month (HAE-specific severe and non-severe)			3.39	Banerji et al. 2017, ³⁰ Longhurst et al. 2017, ³¹ Zuraw et al. 2010 ³²
Number of patients who are attack free in baseline period before starting prophylaxis therapy		Due to drug indications and health plan requirements, this is expected to be minimal or 0.	-	

Distribution of severe attack free months			-	
Proportion of attacks, by severity				
Severe - HAE specific			-	
Severe - All-cause			-	
Non-severe			-	
Treatment administered – Non-severe attacks				
Self			64.9%	Riedl et al, 2015 ³⁴
Home nurse			13.8%	Riedl et al, 2015 ³⁴
Outpatient			21.3%	Riedl et al, 2015 ³⁴
% of severe-HAE specific attacks resulting in hospitalization			40.9%	Zilberberg et al 2011a ³⁵
% of hospitalized patients receiving cricothyrotomy/tracheotomy			40.0%	Bork et al ³⁶
% of cricothyrotomy/tracheotomy patients who receive artificial respiration			40.0%	Bork et al ³⁶
% of hospitalized patients who are intubated			60.0%	Bork et al ³⁶
% of intubated who receive artificial respiration			26.7%	Bork et al ³⁶
% of attacks treated with these on-demand drugs				Assumption in model
Berinert			25%	
Kalbitor			25%	

Firazyr			25%	
Ruconest			25%	
BASELINE HAE-SPECIFIC COST OUTCOMES				
Costs per home nurse			\$179	Graham et al 2017 ³⁷
Costs per physician office visit			\$266	Graham et al 2017 ³⁷
Costs per ED visit			\$1,796	Zilberberg et al 2011a and 2011b ^{35,38}
Costs per hospitalization			\$5,782	Zilberberg et al 2011a and 2011b ^{35,38}
BASELINE HAE-SPECIFIC UTILIZATION OUTCOMES				
Average number of home visits			-	
Average number physician office visits			-	
Average number of ED visits			-	
Average number of hospitalizations			-	

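### Non-severe attacks treated at outpatient sites other than home or office are counted in the attack rate but have no defined cost variable or reported cost

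*Protocol*

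**What the plan says.** **Counting.** Protocol 5.2.1.4 defines a non-severe attack treated by a healthcare professional as "a medical service claim for an on-demand therapy occurring outside an inpatient or ED setting (e.g., physician office"); the office is only an example. Annex 2 repeats the rule without an example: "Any on-demand therapy administered outside an inpatient or emergency room setting will be considered a non-severe attack". Section 5.4.1.1 puts every counted attack into the rate: "Attack rates will be calculated as the total number of attacks in the cohort divided by the number of person-months during baseline".

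**Costing.** Section 5.2.1.5 first gives a general rule: attack costs are the sum over the medical services used in the attack, leaving out on-demand drugs. It then splits non-severe attack costs by location, "home versus office for non-sever attacks", and names two outpatient outputs, the first being "Cost per attack treated with a home visit for on-demand treatment administration" and the second its office-visit counterpart. Annex 2 defines the two matching variables by place of service 'home' and place of service 'office'. Section 5.2.1.6 uses the same two outpatient categories for baseline costs.

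**Reporting.** Annex 3 Table 2 distributes non-severe attacks over self, home nurse and 'Outpatient'. Its cost rows for these attacks are home nurse and "Costs per physician office visit".

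**The concern.** The claims that make an event an attack are a wider set than the claims that give it a cost. An on-demand administration at, say, a hospital outpatient or infusion unit meets the counting rule. It is neither self-treatment nor home nursing, so in Table 2 it can only fall under 'Outpatient'. No cost definition or table row then covers it.

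Section 4 makes both the place of on-demand treatment and the cost of medical care during an attack questions under the primary objective, and says the study is meant to supply updated inputs to the cost-effectiveness model. A model user who takes the 'Outpatient' share from Table 2 finds only one non-home, non-hospital unit cost next to it, the office visit. If other sites make up a real part of that share and differ in cost from an office, the two figures describe different groups of attacks.

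**Working it through.** The study is descriptive on this point and states no sample size or error rate, so the main check is a comparison of the text. The arithmetic only shows how the gap would act.

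**1. Setting by setting**

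| Where on-demand therapy is given | Counted (5.2.1.4, Annex 2) | Table 2 location row | Cost variable (5.2.1.5, Annex 2) | Table 2 cost row |
|---|---|---|---|---|
| Home, by professional | yes | Home nurse | place of service 'home' | home nurse |
| Office | yes | Outpatient | place of service 'office' | physician office |
| Other outpatient site | yes | Outpatient | none | none |

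An administration within five days of an ED visit or hospitalization becomes a severe attack and is not affected. An attack that also has a home or office claim within the five-day window would still receive that claim's cost. The gap is therefore confined to attacks treated only at other outpatient sites.

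**2. Are the Table 2 locations exhaustive?** Earlier-review values: 64.9% (self) + 13.8% (home nurse) + 21.3% (Outpatient) = 100.0%. There is no residual category, so other sites must sit in 'Outpatient'.

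**3. Illustration A: the office cost is used for the whole 'Outpatient' share.** Let f be the fraction of outpatient-treated attacks at other sites and r their cost relative to an office visit. Both are assumptions; the Protocol gives neither. Mean outpatient cost = $266 × (1 − f + f × r).

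- f = 0.30, r = 2: 0.7 × 266 + 0.3 × 532 = $345.80. Using $266 understates by 1 − 266/345.80 = 23%.
- f = 0.30, r = 4: 0.7 × 266 + 0.3 × 1,064 = $505.40. Using $266 understates by 1 − 266/505.40 = 47%.
- r = 1: no bias at any f.
- r below 1: the office figure overstates. The sign depends wholly on r.

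Spread over all non-severe attacks with the 21.3% share, the two understatements are 0.213 × $79.80 = $17 and 0.213 × $239.40 = $51 per attack.

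**4. Illustration B: attacks at other sites contribute no cost.** With every outpatient attack costed as an office visit, mean service cost per non-severe attack = 0.138 × 179 + 0.213 × 266 = 24.70 + 56.66 = $81.36. If a fraction f of the outpatient share adds nothing, the mean is 24.70 + (1 − f) × 56.66:

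| f (assumed) | Mean | Change |
|---|---|---|
| 0.10 | $75.69 | −7% |
| 0.25 | $67.20 | −17% |
| 0.50 | $53.03 | −35% |

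A and B are different mechanisms. The Protocol commits to neither, so neither range is an estimate of the actual error.

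**The case against.** The strongest reply is that nothing sets the cost of other sites to zero. The summing rule in 5.2.1.5 has no place-of-service limit, the list of outputs is not worded as exhaustive, and 5.2.1.6 says costs will be reported by place of service. This stands. A reader might infer that these attacks are explicitly given no cost, and the document does not support that. What it supports is narrower: the location split, the Annex 2 definitions and the table shell leave nowhere for the cost to be captured or shown, so the general rule and its implementation do not fit together.

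Second, the office-visit output is correct as labelled. An office filter measures the cost of an office-treated attack, and the Protocol names no cost per outpatient-treated attack. This also stands; the defect is a missing category, not an error in the existing one.

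Third, a reader might infer that the 'Outpatient' share will be multiplied by the office cost. No section says so. Shares and unit costs are combined in the model, and the Limitations section refers to a separate Model Analysis Plan, which is not at hand. It is also possible that 'Outpatient' in Table 2 is only an inherited label for office care, since 5.2.1.5 uses 'Outpatient care' as a heading over just home and office. The counting rule still admits other sites, however, so the new 'Outpatient' result will contain them if they occur.

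Fourth, the amounts are modest: $17 to $51 per non-severe attack under illustration A, beside the table's $1,796 per ED visit and $5,782 per hospitalization. That limits the importance but does not close the gap.

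Finally, mapping of place-of-service codes is often left to an analysis plan. Here the Protocol fixes the filters itself in Annex 2 and supplies the table shells, so this is a stated definition and can be reviewed as one.

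**Conclusion.** The mismatch holds on the text. Attacks treated by a professional only at an outpatient site other than home or office count in the attack rate and fall in the 'Outpatient' share, but have no defined cost variable or reported output. The office visit cost, the only non-home unit cost beside that share, may not represent it.

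Size and direction are unknown. The Protocol gives neither the frequency of such sites nor their cost relative to an office. The 23% to 47% figures rest on an assumed 30% share and an assumed cost ratio of 2 to 4. The 7% to 35% figures rest on assumed fractions of 0.10 to 0.50 and on the further assumption that no cost is attached. If other sites are rare, or cost about the same as an office, the effect is negligible. The point is worth correcting because it concerns a primary cost question and a model input, and the claims needed to settle it are already identified by the counting rule.

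**What to change.** Define the outpatient attack cost on the same claims as the count: on-demand administration at any place of service other than home, ED or inpatient. Make the change together in 5.2.1.5, the Annex 2 cost definitions and Table 2, and carry it into the baseline cost list in 5.2.1.6. In Table 2, show 'office' and 'other outpatient' as sub-rows, each with its number of attacks, and give the combined mean alongside the 'Outpatient' share. The sub-row counts would also show directly whether the gap matters.

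The cost is one wider place-of-service filter and one or two extra table rows, with no new data. The 'other outpatient' cell may be small in this rare disease; if so, its mean will be imprecise, and the combined row remains the figure to use with the share.

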5.2.1.6 Costs during baseline

Costs will be estimated during a six-month baseline period prior to prophylaxis initiation. Costs will be reported by place of service and by HAE-related health care utilization (minus HAE drug costs) and all-cause utilization. Specific outputs will include:

- Outpatient care
 - Mean total cost of home visits
 - Mean total cost of physician office visits
- Mean total cost of ED visits
- Mean total cost of inpatient hospitalizations

If sample size allows, cost analysis will be restricted to most recent years (2017 – 2020) in order to estimate the most timely and relevant costs. This will be a subgroup analysis of the prophylaxis initiation cohort.

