5.3.1.2 General notes on administrative databases

Electronic outpatient pharmacy dispensing records are considered accurate because pharmacists fill prescriptions with little room for interpretation, and are reimbursed by insurers on the basis of detailed, complete, and accurate claims submitted electronically.^{10,11} Pharmacy dispensing information is usually seen as the gold standard of drug exposure information compared to self-reported information¹² or prescribing records in outpatient medical records.¹³ Drugs used during hospital stays are not recorded in this data source. Prescribing information based on physician notes may overestimate actual medication use because up to 50% of prescriptions are never filled at the pharmacy.¹⁴

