5.4.1.2 Baseline costs (primary objective)

Cost analyses will be based on standard cost amounts reported within the Optum data. Optum's standard costs are based on algorithms that reflect the intensity of care provided, including quantity of services, relative resource costs, and nature of healthcare utilization. Optum's standard costs are an estimate of the allowed amount (i.e., the total cost of the service, and are validated by Optum against the paid amount).¹⁵

All costs will be inflated to 2021 US dollars using Optum's cost factor tables, if 2021 tables are available (typically released in Q2). This method is recommended for Optum data because costs are standardized in multi-year batches.¹⁵ If 2021 tables are not available, costs will be inflated to 2020 US dollars using Optum's cost factor tables and then inflated to 2021 US dollars using the Personal Consumption Expenditure (PCE) price index.¹⁶

Mean values will be reported, along with the standard deviation, median, and inter-quartile range.

To assess sensitivity of results to extreme cost values, additional analyses will be performed where cost values are Winsorized,¹⁷ using the 5th and 95th percentile of the cost distribution as cut points. This procedure involves replacing cost values below the 5th percentile with the 5th percentile value and values above the 95th percentile with the 95th percentile value. Thus, extreme values are pulled in, but the weight on the tails of the distribution is maintained.

If sample size allows, cost analysis will be restricted to most recent years (2017 – 2020) in order to estimate the most timely and relevant costs.

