cricothyrotomy/ tracheotomy	emergency tracheotomy (31603) and an emergency cricothyrotomy (31605)	
Dillon 2013²⁵
 
Esposito²⁶

intubation	The appearance of any of the following encounters CPT - 31500 ICD10 - 09HN7BZ, 0DH57BZ, 0DH58BZ, 0WHQ73Z, 0WHQ7YZ, 09HN8BZ, 0B21XEZ, 0BH13EZ, 0BH17EZ, 0BH18EZ, 0CHY7BZ, 0CHY8BZ ICD9 - 96.04, 96.7x, 96, 96.0,96.5	Pandya 2019²⁷ Singh 2020²⁸ De novo code look up
artificial respiration	The appearance of any of the following encounters Invasive mechanical ventilation: CPT - 94002, 94003, 94004, 94005, E0472, K0534 ICD10 - 5A1935Z, 5A1945Z, 5A1955Z noninvasive ventilation: CPT - 94660, A7027, A7034, A7044, E0452, E0470, E0471, E0601, K0183, K0193, K0194, K0532, K0533 ICD10 - 5A09459, 5A09557, 5A09357, 5A09358, 5A09359, 5A0935B, 5A09457, 5A09458, 5A0945B, 5A09558, 5A09559, 5A0955B ICD9 - 93.90 ventilation NOS: CPT- 94656, 94657 ICD10 - 5A0920Z, 5A0945Z, 5A0955Z, 5A19054, 5A0935Z, 5A09358, 5A0935B,	Pandya 2019²⁷ Singh 2020²⁸ Rosenthal 2020²⁹ De novo code look up
Costs	Algorithm and code lists	Source
Home nurse treatment	Standard cost amount for medical service claims with an on-demand drug administration where the place of service is ‘home’	
Physician office visit	Standard cost amount for medical service claims with an on-demand drug administration where the place of service is ‘office’	
ED visit	Standard cost amount for medical service claims where the type of service is coded as ‘emergency room, professional or facility’	
Hospitalization	Standard cost amount for medical service claims where the type of service is coded as ‘acute inpatient facility’	

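### The promised exclusion of on-demand drug cost cannot be carried out for drugs given during a hospital stay, so the inpatient attack cost may reach the model with the drug still in it

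*Protocol*

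**What the plan says.** Section 5.2.1.5 of the protocol builds the cost of an attack from the medical services used in it, "excluding the costs of on-demand therapies, which are included in the cost-effectiveness model separately". Four outputs follow under that rule: home visit, office visit, ED visit, and "Cost per attack treated as inpatient hospitalization". Section 5.2.1.6 has a parallel rule for the six-month baseline: "Costs will be reported by place of service and by HAE-related health care utilization (minus HAE drug costs) and all-cause utilization". Inpatient stays are among its outputs.

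Three other places bear on whether this can be done:

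- Section 5.3.1.2, on administrative databases in general: "Drugs used during hospital stays are not recorded in this data source".
- Annex 2, Costs: hospitalization cost is the standard cost amount on claims whose type of service is "acute inpatient facility". No step removes a drug component.
- Section 5.4.1.2: Optum's "standard costs are an estimate of the allowed amount (i.e., the total cost of the service, and are validated by Optum against the paid amount".

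The limitations in section 5.4.1.5 do not mention the point. They refer the reader to a separate Model Analysis Plan for the criteria on using attack estimates in the model.

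**The concern.** The study exists to supply inputs to a cost-effectiveness model. The exclusion in section 5.2.1.5 is there to keep on-demand drug cost from entering that model twice, once inside the attack cost and once as its own item. For home and office attacks the safeguard can work, because those attacks are found through claims for the drug's administration and the drug is visible. For an inpatient attack, the protocol's own description of the data says that the drug used in the stay is not there to subtract.

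The model team would then receive an inpatient cost described as net of drug when nobody has netted it and nobody can tell whether it is gross or net. If it is gross and the model adds the drug again, severe attacks look too expensive, averted attacks look too valuable, and the error favours prophylaxis.

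**Working it through.** The protocol states no figure for this quantity, so there is nothing to reproduce. The check has two parts.

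**1. Do the sections fit together?**

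- Rule: on-demand drug cost is removed from every attack cost, inpatient included (5.2.1.5; likewise 5.2.1.6).
- Data: drugs used in hospital stays are not recorded (5.3.1.2).
- Operational definition: the whole standard amount on the acute inpatient facility claim, with no netting step (Annex 2).
- Meaning of that amount: "an estimate of the allowed amount (i.e., the total cost of the service" (5.4.1.2).

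They do not fit. For drug given during the stay, the rule asks for a subtraction with no recorded quantity to subtract, and no section says how else it would be done.

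The gap is confined to the inpatient stratum. Home and office attacks carry a drug claim. The protocol does not say that drugs are unrecorded for ED-only visits. A drug dispensed earlier by a pharmacy, or given in an office within the five-day window of section 5.2.1.4, has its own claim and can still be excluded.

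**2. How large could the double count be?**

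Inputs from Annex 3, Table 2 (prior ICER base case, taken from published sources and not from this database):

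- Cost per hospitalization, C = $5,782
- Cost per ED visit, E = $1,796
- Share of HAE-specific severe attacks hospitalized, h = 40.9%
- On-demand drug shares: Berinert, Kalbitor, Firazyr and Ruconest at 25% each. 4 × 25% = 100% of attacks, with no limit by severity or setting. This fits a model that charges a drug to every attack, but does not prove it.

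Assumed input: s, the share of the inpatient facility amount that is on-demand drug. The documents give no value, so a range of 0% to 75% is shown.

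Formulas, if the model also charges the drug to hospitalized attacks:

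- Double count per inpatient attack = s × C
- Double count per HAE-specific severe attack = h × s × C
- Prior blended cost of a severe attack = h × C + (1 − h) × E = 0.409 × 5,782 + 0.591 × 1,796 = 2,364.8 + 1,061.4 = about $3,426

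| Assumed s | Inpatient cost net of drug | Double count per inpatient attack | Double count per severe attack | As % of $3,426 |
|---|---|---|---|---|
| 0% | $5,782 | $0 | $0 | 0% |
| 10% | $5,204 | $578 | $236 | 6.9% |
| 25% | $4,336 | $1,446 | $591 | 17.3% |
| 50% | $2,891 | $2,891 | $1,182 | 34.5% |
| 75% | $1,446 | $4,336 | $1,774 | 51.8% |

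The figures are illustrative: C is a placeholder for a result that the study has yet to produce.

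**The case against.** A reader might infer more: that the inpatient cost does contain the drug and that the model does add it a second time. The documents do not support that as fact. It needs three things, none of them established:

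- **The facility amount embeds the drug.** Section 5.4.1.2 also says that standard costs come from algorithms reflecting intensity of care and relative resource costs. Such an estimate need not carry the price of a specialty drug.
- **The hospital supplied the drug.** A drug with its own pharmacy or office claim can be removed as planned.
- **The updated model charges a drug to hospitalized attacks.** The 25% shares in Table 2 are the prior review's assumption, and the Model Analysis Plan is not at hand.

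The statement that inpatient drugs are unrecorded can also be questioned. It sits among remarks on outpatient dispensing records, and Annex 2 identifies HAE-specific inpatient or emergency events partly by administration of on-demand treatment. The protocol therefore expects to see some administrations on such events.

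Sizing the problem by the full price of a drug course would also be unsound. The documents give no price, and a component cannot exceed the stay cost that contains it.

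These objections stand against any claim of a proven double count or a fixed dollar amount. They do not remove the mismatch. Administrations visible on some severe events do not provide a netting step for drug inside a facility amount, and no section reconciles 5.2.1.5 with 5.3.1.2 and Annex 2. Even if s is zero, the text promises a step that the data as described cannot support.

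**Conclusion.** The point holds as an inconsistency with a conditional consequence. The inpatient attack cost, and the inpatient part of the HAE-related baseline cost, cannot be made net of on-demand drug given during the stay, yet both are described as net. Double counting, and the resulting tilt towards prophylaxis, follows only if the facility amount includes the drug and the model adds drug cost to hospitalized attacks. The phrase describing the standard amount as total service cost supports the first condition, and drug shares covering 100% of attacks suggest the second. Neither is proved.

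The size is open from zero upwards: up to about $4,336 per inpatient attack and $1,774 per severe attack at the top of the assumed 0% to 75% range. Both figures rest on prior base-case inputs. The matter should be corrected because it attaches a property to a model input that the study cannot deliver.

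**What to change.** - In 5.2.1.5 and 5.2.1.6, keep the exclusion for every separately billed on-demand drug line in any setting, including lines within the five-day window of a hospitalized attack. Restricting the exclusion to non-inpatient attacks would leave such lines inside a hospitalized attack's cost.
- In the same sections and in Table 2, state that the inpatient facility cost is not netted of drugs given during the stay. Wording such as not netted is safer than gross, because the drug content is unknown.
- Add this to the limitations in 5.4.1.5.
- Give the model team a sensitivity analysis with and without a separate on-demand drug cost for hospitalized attacks. Both runs are needed: adding the drug double counts if the facility amount contains it, and omitting it undercounts if it does not.

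The cost is a few sentences, one table label and one sensitivity run. No new data are needed.
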